Tableau Clinician Auditing and Feedback Report

A feedback report will be developed by HCA Healthcare corporate IT, using Tableau, an electronic based platform that has been used several of our previous HCA Healthcare multi-center trials. The feedback report will provide facility level data on acceptance of the CPOE risk estimate prompt empiric antibiotic recommendations and evaluate broadly, "at-a-glance", what acceptance rates are among clinicians at the site.

The intent of the report is for local Study champions to feed back to local clinicians on acceptance of the CPOE risk estimate prompt empiric antibiotic recommendations. Study Champions will be educated via webinars on how to use the Tableau dashboard, interpret the data, and compile reports to feed back to prescribing clinicians. Summaries can be viewed at the facility and clinician level ES antibiotic selection by indication. Several filtering options will be available on the Tableau Report for Study Champions or other local users to compare and track clinician acceptance or non-acceptance of the CPOE risk estimate prompt recommendations.

Several filtering options will be available on the Tableau Report for Study Champions or other local users to compare and track clinician acceptance or non-acceptance of the CPOE risk estimate prompt recommendations:

- Acceptance and Non-Acceptance Summary Reports Study Champion can use this filter to look at overall acceptance or non-acceptance of empiric antibiotic recommendations.
 - This summary level report will be available as an initial view of overall acceptance or non-acceptance for (1) clinician-level and (2) hospital-level acceptance (compared to other Arm 2 facilities). It will allow for range filtering for viewing data across designated periods of time that allows trending.
 - This option will be available for viewing/printing summary tables and graphs with deidentified clinician information.
 - This report will be able to be filtered by initial antibiotic ordered.
- Antibiotic Prescribing Per Protocol defined as # (%) of per-protocol antibiotic prescribing
 among patients with SST Infections. This gives clinicians credit for choosing standard-spectrum
 antibiotics that never required a trigger in the risk estimate prompt.
- Emergency Department (ED) ICU-Bound Prompt Report INSPIRE CPOE workflow includes a prompt to ED clinicians asking if the patient is ICU-bound. If response is "yes" then no further CPOE screens will fire. This report allows study champions to see how often ED clinicians respond "yes" to assess whether clinicians may be circumventing the prompt.
- **Prompt Report** This report provides the # or % of opportunities that results in a CPOE risk estimate prompt activation.
 - Allows filtering by prompt action chosen (cancel, override, replace)

- Override Report Some pharmacists may want to be able to filter by type of override for intended follow up plan that day. They may know they are going to round in the ICU, they may want to print out a list of all overrides due to ICU-bound and check to see if they actually went to the ICU while they were there, or they may be doing medication reconciliation with allergies and want a printout of all the overrides due to allergies and cross check those simultaneously.
- Extended-Spectrum (ES) Indications Report For use if Study champion would like to organize by ES antibiotic orders and by indication.

F. Study Schedule

The timeline for the trial is shown in Figure 3 below, with key milestones indicated.

Figure 3. INSPIRE-ASP Trial for Skin and Soft Tissue Infections Timeline: 6/2020 - 5/2025

	Year 1			Year 2			Year 3				Year 4				Year 5					
	(6/20	- 5/2:	1)	((6/21 - 5/22)			(6/22 - 5/23)				(6/23 - 5/24)				(6/24 - 5/25)			
MILESTONE	Q1	Q2	Q3	Q4	Q1	Q2	Q3	Q4	Q1	Q2	Q3	Q4	Q1	Q2	Q3	Q4	Q1	Q2	Q3	Q4
Facility Recruitment																				
Randomization with Baseline																				
Characteristics																				
Committee Approvals																				
Coaching Calls																				
Site Visits																				
Distribute Toolkit																				
Phase in (5-month)																				
Intervention (12-month)																				
Clinician Feedback Reports																				

G. Assessment of Outcome Measures

G.1. Data Sources and Collection

Trial data will not be collected by participating sites. Instead, all variables and outcomes will be obtained from custom extractions from the HCA Healthcare computerized data warehouse. HCA Healthcare has a long-established corporate data warehouse with admission data, demographics, diagnostic and procedure codes, CPOE data, and laboratory and pharmacy data. Trial data from the computerized data warehouse will include demographic, insurer, comorbidity, and laboratory (including microbiology) data for SST infection cohorts.

G.2. Specifications of the Appropriate Outcome Measures

The primary, secondary and safety trial outcomes are summarized below in Table 3.

G.3. Primary Outcome Measures

The primary trial outcome for SST infections reflects the national metric of days of therapy (DOT) of extended-spectrum antibiotic use (ES-DOT), which we will evaluate for the empiric period (hospital day 1-3). Trial success will be based upon the relative reduction in this metric between the INSPIRE Stewardship Bundle vs routine care arm when accounting for baseline values.

G.4. Secondary Outcome Measures

There will be one secondary outcome for SST infections (antipseudomonal antibiotic days of therapy).

G.5. Safety Outcomes

Two safety outcomes will also be assessed. We will evaluate if increased use of standard-spectrum antibiotics causes increased ICU transfers or hospital length-of-stay.

Table 3. Trial Outcomes

Outcome	Metric for SST infection Cohorts
Primary Trial Outcome: Total Empiric Extended-Spectrum Antibiotic Days of Therapy (ESDOT)	The number of different extended-spectrum antibiotics each empiric day, summed across the first 3 days of hospitalization. ¹
Secondary Trial Outcomes: Total Empiric Antipseudomonal Antibiotic Days of Therapy (ES-DOT)	The number of different antipseudomonal antibiotics each empiric day, summed across the first 3 days of hospitalization. 1,2
Safety Outcomes: ICU Transfer	Intensive Care Unit (ICU) Transfer: Days to ICU transfer, from hospital days ≥ 3 and ≤ 14
and Length-of-Stay	Length-of-stay: Days from hospital admission until discharge or hospital day 14, whichever comes first, where admission day is hospital day 1.

¹E.g., if a patient is admitted for 2 days, ES-DOT will be calculated across those 2 days; however if a patient is admitted for 4 days, only the first 3 days will be evaluated.

H. Statistical Considerations

H.1. Criteria for Discontinuation or Withdrawal

As a pragmatic trial of a quality improvement protocol, follow-up of the analytic cohort will be assured. It will involve the entire hospitalization as recorded in the electronic health record. Drop-outs will not be applicable at the patient level.

Hospitals can withdraw participation at any time. New antibiotic stewardship interventions affecting prescriptions in the empiric period or changes in EMR system that affect antibiotic order entry (e.g., Patient Keeper, Meditech Expanse) will be assessed by the steering committee for possible conflict and withdrawal of participation (for as treated analyses) during the trial. All participating facilities (via the Study Champion) will report any new proposed initiatives via the study email or in response to a standing polling question on every coaching call. Sites will be trained to understand why competing interventions could jeopardize the findings of the study. Should the Steering Committee identify a conflict, we may report back to the Study Champion to request the facility delay implementation of the new initiative until the trial has ended. If the facility is unable delay implementation, we will conduct an analysis at the end of the trial to assess the impact of interventions on the trial outcomes, or if the impact to the trial is significant, the facility may be asked to drop from the trial (for as treated analysis).

H.2. Study Outcome Measures

See Section G. above.

H.3. Analysis Plan

Primary Statistical Analysis

The primary trial outcome is defined as the summed number of different ES antibiotics received during each empiric day. An empiric day is a day within the first three days of an admission. We define this outcome as the Total Empiric Extended-Spectrum Days of Therapy (ES-DOT). For clarity, the calculation is as follows: we define a DOT for a particular ES antibiotic as a day in which any number of doses of that antibiotic is given. Different ES antibiotics are summed within each empiric day for each patient admission to determine DOT in that at-risk day. Antibiotics given during an associated emergency department visit on the date of hospital admission are counted toward the ES-DOT of the first hospital day.

²Does not include aminoglycosides or fluoroguinolones

The main trial results will be based upon as-randomized, unadjusted analyses of admission-level ES-DOT. In contrast to the national DOT measure defined by CDC for hospitals, we define ES-DOT at the individual admission level so that we can perform analyses on individuals.

The trial will be assessed among the cohort of adult admissions who: 1) have administrative claims codes indicating an SST infection is present on admission; 2) received any antibiotic within 3 days of admission; and 3) were admitted to a non-ICU location. For admissions initially on a non-ICU floor and transferred to the ICU, analysis will include only admission days on the non-ICU floor within 3 days of admission.

The trial periods are defined as follows: (1) Baseline: January 1, 2019 – December 31, 2019 (12 months); (2) Phase-in: August 2, 2022 – December 31, 2022 (5 months, does not contribute to analysis); (3) Intervention: January 1, 2023 – December 30, 2023 (12 months). The main evaluation of all outcomes will be difference-in-difference between the Intervention and Baseline periods and between study arm. Trial analysis will use a baseline period prior to the arrival of the COVID-19 pandemic since hospital operations and case mix were severely impacted by this pandemic between Winter 2020-Spring, 2022. ²⁵⁻²⁹ Although at the time of this writing (June, 2022), COVID-19 surges continue to occur nationally, clinical operations and patient case mix at most hospitals have largely returned to near pre-pandemic activity in the setting of widespread vaccination and milder virus strains. Phase-In is scheduled for August, 2022 as participating hospitals are in a state of recovery sufficient to launch the trial intervention with pharmacy/physician engagement.

The unit of analysis will be individual admissions. Individuals can contribute more than one admission. The analytic model will be a generalized linear mixed effects model for differences in differences, with random effects accounting for correlation within cluster, period-varying random effects to allow for differences within hospitals between baseline and follow-up, and admission-level random effects to account for correlation within person and hospital, if sufficient data exist. We plan to use a Poisson model for analysis of outcomes as follows:

$$log\big(y_{ijph}\big) = \beta_0 + \beta_1 A_{ijph} + \beta_2 T_{ijph} + \beta_3 A_{ijph} T_{ijph} + b_{0h} + b_{1h} T_{ijph} + g_j + \log\ (ed_j)$$

where y_{ijph} is the ES-DOT for patient i for admission j in period p at hospital h, and $A_{ijph}=1$ if hospital h is in the intervention arm and 0 if not, and $T_{ijph}=1$ if p is the intervention period and 0 if baseline period. The random effects b_{0h} and b_{1h} allow for different baseline mean admission-level ES-DOT for each hospital and each hospital in the intervention period, respectively. Equivalently, they allow for correlation within hospital at different levels at baseline and at follow-up. The random effect g_j allows each patient to have a different mean ES-DOT. Finally, ed_j is the number of empiric days in the admission.

ES-DOT. Finally, ed_i is the number of empiric days in the admission. The assessment of trial success will be determined by the significance of the arm by period interaction term β_3 , which assesses whether the log relative rate of the outcome due to being in the intervention arm in the intervention period is different from 0. The exponentiated parameter estimate for β_3 is the estimated relative rate of ES-DOT per at-risk day due to the intervention, relative to the baseline period. For example, if β_3 had a negative value and a p-value <0.05, we would conclude that the patient-specific CPOE smart prompts generated a benefit over routine care. Exponentiating the parameter value would provide an estimate of the relative reduction due to the intervention in the expected ES-DOT per at-risk day.

The primary trial analysis will use an as-randomized unadjusted model with two-tailed significance set at alpha = 0.05. Secondary outcomes will be assessed using an as-randomized unadjusted model and will include adjustment for multiple comparisons with two-tailed significance set at alpha = 0.025 for the two secondary outcomes.

Subsequent analyses of the primary and secondary outcomes will include both as-treated and adjusted models. Adjusted models will account for individual characteristics such as age, gender, comorbidities, and prior history of MDROs as well as hospital characteristics such as hospital antibiotic resistance. We will also account for seasonality. All adjusters will be determined a priori. These analyses will be reported as point estimates with confidence intervals and without p-values. The reason for including these analyses is to provide additional information related to the trial outcomes for readers to assess the effects of potential confounders. The reason to not include them in a formal multiple comparisons adjustment is because these analyses are non-independent evaluations relative to the as-randomized unadjusted analyses.

We will separately evaluate intervention period effects by arm alone.

Safety Outcomes

Safety outcomes noted in the above table will be assessed in the most conservative manner to identify potential safety issues. Safety outcomes are required because a reduction in ES-DOT might be achieved only by incorrectly withholding ES antibiotics when they were really needed. Each safety outcome will be evaluated for non-inferiority using an as-randomized unadjusted analysis with a one-tailed significance set at alpha = 0.05. Length-of-stay and days to ICU transfer are evaluated within 14 days of admission since empiric antibiotic selection within the first 3 hospital days is not expected to be a main driver of either outcome beyond this time period; evaluation of baseline data also shows that 91% of SST patients have length-of-stay equal to or less than 14 days. Analyses planned for these assessments are proportional hazards models with random effects for each hospital and admission These models are sometimes called frailty or shared frailty models. Because these are safety outcomes, we do not intend to make adjustments for multiple comparisons in testing them, further increasing conservatism.

All analyses will be performed using current versions of SAS (Version 9.4, as of writing, SAS Institute, Cary NC) and/or R (Version 4.0, as of writing).

C.2.11 Power Size/Sample Size Calculations

Power assessment proceeded as follows, using a Monte Carlo approach.²⁵ We used available data to define a baseline period of 1/1/2019-12/31/2019. In a bootstrap procedure, individuals were selected with replacement from within each hospital, once to represent baseline data and separately to represent "intervention period" data. Hospitals were then "randomized" to intervention or control according to multiple parameters, including number of admissions with SST infection and ES-DOT. We then modified the outcomes for the bootstrapped individuals in the "intervention" period in the "intervention" arm to reflect the effect of the intervention.²⁹

We assessed power to identify an overall 12.5% relative reduction in ES-DOT. This effect was implemented by reducing the relative empiric days of therapy for each admission which was exposed to the CPOE prompt. The amount of reduction was a uniform random variate between 0.75 and 1. For example, if the bootstrapped patient initially received 8 ES-DOT and was assigned to have a have a 12.5% reduction, then that admission intervention ES-DOT would be reduced to 7 days. The reduction of ES-DOT was selected with a lower bound determined by the investigators as the minimal effect achieved that would be clinically meaningful. Using this method, we have ≥99.9% (99.6-99.9%) power to detect this effect.

Since adoption of the intervention will be heavily influenced by the ability to demonstrate safety, our study size was based on the power to detect non-inferiority for safety outcomes. We used methods similar to the above to calculate the power to identify at least a one day increase in length-of-stay for 12.5% of patients who had hospitalizations less than 14 days and found the power was 68.9% (CI 65.9-71.8%), where non-inferiority is defined as a hazard ratio no smaller than 0.98. For days to ICU transfer, we estimated the power to detect a 2% increase in transfers to the ICU on hospital day 3 through 14 to be >99.9% (CI 99.6-99.9%), where non-inferiority is defined as having a hazard ratio no greater than 1.1 (fewer days to ICU results in a hazard ratio above 1).

For completeness, we note that there are other pre-specified outcomes intended for exploratory analysis in secondary papers for the INSPIRE ABD trial in Table 4 below.

Table 4: Secondary Manuscripts - Other Pre-Specified Outcomes

Secondary Manuscripts (other pre-spe-	cified secondary exploratory analyses for later manuscripts)
	The number of different ES antibiotics received each day, on
Therapy after the Empiric Period	hospital days ≥4 and ≤14.

Empiric and Total Antibiotic Costs	Empiric and total antibiotic costs during hospitalization
Incidence of Hospital-Onset C. difficile	Hospital-onset C. difficile positive tests (specimen obtained) on
incidence of Hospital-Oriset C. difficile	hospital days ≥4 and ≤14.
Incidence of Hospital-Onset MDRO-	Newly-detected hospital-onset MDRO-positive cultures on
positive Cultures	hospital days ≥4 and ≤14. Includes total MDRO and specific
positive Cultules	MDRO subsets.

I. Access to Source Data/Documents

To protect the large volume of protected health information required for the INSPIRE-ASP SST Infections Trial, HCA Healthcare will establish a mechanism similar to our previous trials where the study's programmer analysts gain access to HCA Healthcare data behind the HCA Healthcare firewall. Programmer analysts will receive remote access to an HCA Healthcare web server where requested data will be placed after extraction by HCA Healthcare information technologists. This extraction process will involve replacement of names and medical record numbers with coded identifiers. Programmers will access this virtual machine to clean and analyze data, and to generate summary level output for review with our statistician.

J. Quality Control and Quality Assurance

Monthly data will be accessed by study data analysts from the HCA Healthcare CDW behind their corporate firewall. We anticipate extracting data monthly to be able to validate the data streams. Data stream validation involves initial validation by HCA Healthcare to ensure the integrity of data capture and transfer from individual hospital electronic data systems to the HCA corporate centralized data warehouse. This will occur under general HCA Healthcare operations and has a <<1% error rate.

The study programmer analysts will assess each data element for variation within and across hospitals within individual streams. Data cleaning will involve assessing missing data and unusual month-to-month variation in data elements. Data discrepancies will be resolved by revised data extraction methods, particularly those requiring multiple data streams, and by performing quality control checks on the programming code.

K. Subject Confidentiality

K.1. Future Use of Stored Specimens

This study will not include any stored specimens.

K.2. Subject Confidentiality

To protect the large volume of protected health information required for the INSPIRE-ASP SST Infections Trial, study programmer analysts will gain access to HCA Healthcare data behind the HCA Healthcare firewall. Programmer analysts will receive remote access to an HCA Healthcare web server where requested data will be placed after extraction by HCA Healthcare information technologists. This extraction process will involve replacement of names and medical record numbers with coded identifiers. Programmers will access this virtual machine to clean and analyze data, and to generate summary level output for review with the study's statistician.

L. Ethics /Protection of Human Subjects

L.1. Centralized Institutional Review Board (IRB) Process and Prior Experience

As a pragmatic cluster-randomized trial of an antibiotic stewardship quality improvement strategy, we will request a minimal risk determination consistent with our prior HCA Healthcare clinical trials. Reasons supporting a minimum risk determination are: 1) the protocol is guideline-concordant, 2) prompts provide risk estimates and recommendations, but does not supplant clinical judgment, 3) evidence suggests that there is time to wait for culture results in non-ICU patients instead of using empiric extended-spectrum antibiotics for uncommon resistant organisms.

Similar to all prior HCA Healthcare clinical trials, the Harvard Pilgrim Health Care (HPHC) IRB will approve a centralized IRB protocol and coordinate reliance agreements with participating hospitals with support from HCA Healthcare's corporate regulatory affairs liaison ([name] MBA, Vice President, Research Compliance and Integrity). In prior trials, IRB approval can be obtained within 2-3 months and the reliance process can occur in a rolling fashion during recruitment, overall requiring an additional 3-4 months.

L.2 Informed Consent Process

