The rationale for including only the first three days of the admission is that this is when the actual status of the patient with respect to the need for an ES antibiotic is unknown. Bearing this in mind, antibiotics given during an associated emergency department visit on the date of hospital admission are counted toward the ES-DOT of the first hospital day.

The trial baseline period includes January 1, 2019 – December 31, 2019 (12 months). The intervention period includes January 1, 2023 – December 31, 2023 (12 months). The baseline was selected to include time prior to the arrival of the COVID-19 pandemic since hospital operations and case mix were dramatically affected between Winter 2020-Spring, 2022. ¹⁻⁴ Although COVID-19 surges have continued to occur, clinical operations and patient case mix at most hospitals have largely returned to near pre-pandemic activity. We considered that a state of pre-pandemic normalcy returned by summer of 2022, and introduced our intervention on August 2, 2022. The period between then and December 31, 2022 is considered a phase-in period and is not used in trial evaluation.

Primary Statistical Analysis

The primary trial outcome is defined as the summed number of different ES antibiotics received during each empiric day, on the patient-admission level. An empiric day is a day within the first three days of an admission. We define this outcome as the Total Empiric Extended-Spectrum Days of Therapy (ES-DOT). For clarity, the calculation is as follows: we define a DOT for a particular ES antibiotic as a day in which any number of doses of that antibiotic is given. Different

ES antibiotics are summed within each empiric day for each patient admission to determine DOT in that at-risk day.

The main trial results will be based upon as-randomized, unadjusted analyses of admission-level ES-DOT. We note that the national DOT measure defined by CDC is measured at the hospital level. We define ES-DOT at the individual admission level so that we can perform analyses on individuals.

The main evaluation of all outcomes will be based on the difference in differences between the intervention and baseline periods and between study arms.

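### The power simulation gives hospitals no change of their own between 2019 and the intervention period, so the stated powers are best-case values; length of stay (68.9%) is the one materially exposed

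*Protocol*

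**What the plan says.** Protocol C.2.11 describes a bootstrap power calculation. Its source is a single year: "We used available data to define a baseline period of 1/1/2019-12/31/2019". Within that year, "individuals were selected with replacement from within each hospital, once to represent baseline data and separately to represent" the intervention period. Hospitals are then allocated to arms, and outcomes are altered only for intervention-arm admissions in the second period. For ES-DOT the alteration is a random multiplier drawn separately for each admission exposed to the prompt. No hospital-specific change between periods is described.

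The result for ES-DOT is "Using this method, we have ≥99.9% (99.6-99.9%) power to detect this effect". By similar methods the section reports 68.9% (65.9 to 71.8%) for length of stay, with a hazard ratio margin of 0.98, and more than 99.9% for ICU transfer, with a margin of 1.1. It says that the study size rests on the safety powers.

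The primary model in Protocol H.3 includes "period-varying random effects to allow for differences within hospitals between baseline and follow-up", and the SAP's primary model has the same term. For the safety outcomes, Protocol H.3 names random effects for hospital and admission only. The SAP's Safety Outcomes section adds time period, without saying whether that effect is specific to each hospital.

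The real second period is 2023. The SAP (Data Collection Details) states: "The intervention period includes January 1, 2023". Of the years between, it says that "hospital operations and case mix were dramatically affected between Winter 2020-Spring, 2022".

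**The concern.** Two resamples of one hospital-year differ only by sampling noise and the injected effect. The simulated trial therefore has no variation between hospitals in how they change over time, which is the variation that the primary model's hospital-by-period term exists to capture. Nor does it have a hospital-level spread in acceptance of the prompt, although the feedback reports (Protocol E.2.2) are built to compare acceptance between hospitals.

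In a difference-in-differences analysis of clusters, more admissions do not reduce this variance. It is divided only by the number of units, 46 per arm. With a margin as tight as 2% on the hazard ratio, even modest drift can matter. The Protocol says that adoption will depend heavily on showing safety. A missed non-inferiority margin for length of stay would then be read against a power that left out a source of variance the plan itself recognises.

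**Working it through.** **1. What the printed intervals cover.** The exact 95% binomial interval for 689 successes in 1,000 is 65.9 to 71.8%, as printed. For 1,000 in 1,000 the lower limit is 99.6%, also as printed. The intervals therefore match Monte Carlo error from about 1,000 replicates and carry no uncertainty about the variance assumptions.

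**2. The missing term.** Let SE0 be the standard error from sampling within hospitals, which is what the bootstrap generates. With 46 units per arm,

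SE = √(SE0² + 2τ²/46).

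At τ = 0.05 the added part is √(2 × 0.0025/46) = 0.0104.

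**3. Can 68.9% be reproduced?** Inputs: 61,000 admissions in the intervention period (Protocol, Brief Overview), assumed equal at baseline; 30,500 per arm and period; 91% discharged by day 14 (Protocol H.3), so 27,755 events per cell. Then SE0 = √(4/27,755) = 0.0120.

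- Non-inferiority at a true hazard ratio of 1: Φ(−ln 0.98/0.0120 − 1.645) = 51.5%. With two arms and one period, SE0 = √(2/27,755) = 0.0085, giving 76.9%.
- Detecting harm: assumed length-of-stay distributions with 91% discharged by day 14 give hazard ratios of about 0.970 to 0.979 for the stated one-day shift. Φ(−ln HR/0.0120 − 1.645) then runs from 81% down to 55%.

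The stated figure is compatible with the second reading, but the documents do not allow it to be reproduced on either.

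**4. Length of stay, anchored at 68.9% when τ = 0.** The z-values sum to 1.645 + 0.493 = 2.138.

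- Detecting harm: SE0 = 0.0120, so the implied log effect is 0.0120 × 2.138 = 0.0257 (hazard ratio about 0.975).
- Non-inferiority at a hazard ratio of 1: −ln 0.98 = 0.0202, so the implied SE0 is 0.0202/2.138 = 0.0094.

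Power = Φ(effect/SE − 1.645):

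| τ | Detecting harm | Showing non-inferiority |
|---|---|---|
| 0 | 68.9% | 68.9% |
| 0.03 | 60% | 55% |
| 0.05 | 49% | 42% |
| 0.10 | 28% | 22% |

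**5. If the safety model has no hospital-by-period term.** The reported standard error stays at SE0 while the true one is SE. Power is Φ((effect − 1.645·SE0)/SE) and the actual one-sided error is Φ(−1.645·SE0/SE). Ranges cover the two values of SE0.

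| τ | Power | One-sided error (nominal 5%) |
|---|---|---|
| 0.03 | 66–67% | 7–9% |
| 0.05 | 63–65% | 11–13% |
| 0.10 | 58–60% | 21–25% |

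**6. ES-DOT.** The effect is −ln 0.875 = 0.1335. With an assumed coefficient of variation of 1.2 per admission, SE0 = 1.2 × √(4/30,500) = 0.0137. Power = Φ(0.1335/SE − 1.96):

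| τ | Formula | Simulation of 2 × 46 units |
|---|---|---|
| 0.10 | 99.96% | 100% |
| 0.15 | 97% | 97% |
| 0.20 | 86% | 85% |
| 0.25 | 70% | 69% |

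Power drops below 99.9% only above τ of about 0.11 (about 0.06 to 0.12 for coefficients of variation from 2.0 down to 0.8).

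**7. ICU transfer.** If the 2% increase means two percentage points on an assumed 1 to 3% rate, power stays above 99.9% even at τ = 0.3. The text does not say whether 2% is absolute or relative.

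**The case against.** A reader might infer that every printed power is materially wrong. The documents do not support that. The direction is the same for all three, but ES-DOT keeps its printed value up to τ of about 0.10, and ICU transfer may hardly move.

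A reader might also infer that the event-count standard error alone explains 68.9%, leaving no room for other variance. That depends on the harm reading and on one hazard ratio picked from a range giving 55 to 81%. The planned test is non-inferiority against 0.98, and there the same standard error gives 51.5%. C.2.11 also does not say how many admissions were simulated.

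Three further objections have weight. First, the length-of-stay reductions assume an analysis that estimates hospital-by-period variance, and the Protocol's safety model does not. This stands, and it changes the consequence rather than removing it: power falls less, but the error rate rises. Second, the simulated effect applies to prompted admissions, whose share can differ by hospital, so some between-hospital spread in effect may already be present. Only the spread in acceptance is clearly missing. Third, the Protocol and SAP also say that operations and case mix at most hospitals had come back close to pre-pandemic levels, and drift common to all hospitals is absorbed by the period term. That is correct; only differential drift counts, and its size is unknown. A broad recovery does not make it zero.

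Finally, the SAP is dated after the intervention period and fixes the margins, so pre-trial power will not decide the safety result. That limits the consequence to interpretation and to the specification of the safety model.

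**Conclusion.** The concern holds in a limited form. The simulation sets hospital-by-period variance to zero by construction, so the three powers are best-case values in that respect and their intervals understate the uncertainty. Length of stay is materially exposed: an SD of 5% in hospital-specific change takes 68.9% to 49% or 42%, depending on what the figure means, if the analysis accounts for the variance. If it does not, the one-sided error is about 11 to 13% at the same τ. Because 68.9% is above one half, any τ above zero lowers it on either reading.

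The size rests on a τ that the documents do not supply, on equal numbers of admissions in the two periods, and on a normal approximation anchored to a figure that cannot be reproduced. The ES-DOT results also rest on an assumed outcome variance. For ICU transfer the effect is not established, and it is small if the 2% is absolute.

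**What to change.** Rerun the bootstrap with a unit-by-period shift over a stated range of τ. Inform the range from different calendar years already in the warehouse; Protocol E.2.1 refers to three years of data for the risk models, without naming the years. Include a wider value as well, because adjacent years may understate drift from 2019 to 2023. Add a between-hospital spread to the injected effect.

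Analyse the simulated trials with a hospital-by-period term in the safety models as well as in the primary model, and write that term explicitly into the SAP's Safety Outcomes section. State whether 68.9% is power to show non-inferiority or to detect harm, and whether the 2% for ICU transfer is absolute or relative. Restate the three powers with the assumed τ beside each, and label the printed intervals as simulation error. Do not change the sample size.

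The cost is a few hours of simulation on data already held, and stated powers that look less favourable.
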